- **Treatment Period (Day 1 to Day 24):** Four weekly dose sessions, with associated remote sessions. The dose sessions will last at least 8 hours, and until all effects (physical and psychological) have resolved (whichever is longer). Each dose session will be followed by a safety phone call 1 day after dosing and efficacy assessments 2 days after dosing. Each dosing period will be recorded for quality and training purposes. The recordings may be reviewed to ensure the dosing session monitor is adhering to the dosing session monitor training.
- **Follow-Up Period (Day 29 to Day 64):** Follow-Up visits for safety and efficacy will occur at 1, 2, 3 and 6 weeks post-final study drug administration. In addition, there will be Reflection Sessions 1, 2 and 3 weeks post-final study drug administration. Participants will be contacted via telephone on Day 57 ( $\pm$ 2 days) for Follow-Up.

The expected duration of participation for each participant who completes all study visits, from Screening to the EOS visit, is up to 16 weeks.

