### 1.2 Study Design Schema

Screening (Up to 28 days)		Treatment Period (4 weeks) (methylone [Part A]; methylone or placebo [Part B])												Follow-up (6 Weeks)				
Day -28 to Baseline	Day -4 to Day -1	Treatment #1			Treatment #2			Treatment #3			Treatment #4			Day 29	Day 36	Day 43	Day 57	Day 64
Screening visit	Baseline / Preparatory Session	Day 1	Day 2	Day 3	Day 8	Day 9	Day 10	Day 15	Day 16	Day 17	Day 22	Day 23	Day 24	Efficacy/ Safety / Reflect session	Efficacy/ Safety / Reflect session	Efficacy/ Safety / Reflect session	Phone visit: Safety	Efficacy/ Safety Assessments
		In-clinic: Dose Session	Phone visit: Safety	Efficacy / Safety Assessments	In-clinic: Dose Session	Phone visit: Safety	Efficacy / Safety Assessments	In-clinic: Dose Session	Phone visit: Safety	Efficacy / Safety Assessments	In-clinic: Dose Session	Phone visit: Safety	Efficacy / Safety Assessments					

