### 1.3 Schedule of Assessments (SoA)

	Screening		Treatment Period												Follow-Up Period					ET
Visit Number	1	2	3	4	5	6	7	8	9	10	11	12	13	14	15	16	17	18	19	-
Visit Session	ScrN	BL/ Prep	Treatment 1			Treatment 2			Treatment 3			Treatment 4			FU1	FU2	FU3	TC	FU4 /EOS	ET visit
Study Day(s)	-28 to BL	-4 to - 1	1	2	3 (+1)	8 (±1)	9	10 (+1)	15 (±1)	16	17 (+1)	22 (±1)	23	24 (+1)	29 (±1)	36 (±2)	43 (±2)	57 (±2)	64 (±3)	-
ICF	X																			
Demography	X																			
Confirm Eligibility	X	X	X																	
Med Hx	X																			
Substance Use Hx	X																			
Drug Use Assessment 	X	X	X			X	X		X			X								
Pregnancy Test 	X		X			X	X		X			X			X					X 
Physical Exam	X 														X				X 	X 
Vital Signs 	X	X	X 			X 			X 			X 			X					X 
12-Lead ECG	X		X 			X 			X 			X 			X					X 
Clinical Labs 	X								X						X					X 
MINI (central rater)	X																			
LEC-5	X																			
SPQ	X																			
SCID-5-PD (Central rater) 	X																			
CAPS-5 (past month; central rater)	X																			
C-SSRS 	X	X	X	X	X	X	X	X	X	X	X	X	X	X	X	X	X	X	X	X
Preparatory Session 		X																		
Randomization 			X																	
Study Drug Admin 			X			X			X			X								

 Urine drug screen must be confirmed as negative prior to enrollment and each dose. Site must confirm patient is not otherwise impaired prior to dosing.

 Urine test for WOCBP only. Pregnancy test must be confirmed as negative prior to enrollment and each dose. Serum FSH may be conducted at Screening to confirm non-childbearing potential.

 Only required if the ET visit occurs prior to the Day 29 visit.

 Height and weight will be collected at Screening; weight will be conducted at the end of study.

 Includes heart rate, blood pressure, and temperature.

 Vital signs during the dose session: BP and HR - predose, every 30-minutes post-initial dose, and prior to the booster dose; temperature- predose (within 10 min), and every 60 minutes.

 ECGs will be captured predose and at the end of the dosing session.

 Clinical labs will be assessed by a central lab.

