Study Visit	Visit Timing	Brief Description of Events
Dose Session 1 (Visit 3 – Within 4 days of Baseline/ Preparatory Session	Day 1 – Predose	
Prior to enrollment (Part A) or randomization (Part B), an eligibility criteria review, a negative urine pregnancy test (WOCBP only), and urine drug screen will be required. Once confirmed that the participant meets all criteria, they will be enrolled (Part A) or randomized (Part B) onto the study. Predose assessments will then be performed (including vital signs, temperature, 12-lead ECGs, and C-SSRS).
 
Participants should have fasted (water only) for at least 2 hours prior to dosing and for at least 2 hours after the booster dose.
 
(Methyl) xanthine- and caffeine-containing products should be avoided for 2 hours predose until at least 8 hours after the initial dose.

	Day 1 – Dose Session 1 (~8 hours)	
Recording begins immediately prior to dosing.
 
Following dosing, adverse event monitoring begins.
 
The open-label treatment for Part A is:
 
 
Methylone 150 mg, with a booster administration of 100 mg administered 90 (±10) minutes later.
 
 
The two blinded study treatment arms for Part B are:
 
 
Methylone 150 mg, with a booster administration of 100 mg administered 90 (±10) minutes later.
 
Matched placebo (initial and booster).
 
 
Safety will be assessed at the following timepoints during the dose session:
 
 
BP and HR will be recorded 10 minutes predose and at 30-minute intervals (±15 minutes) post-administration until the end of the dose session 
 
In addition, BP and HR will be recorded within 15 minutes (+5 minutes) prior to administration of the booster dose (equivalent of 90-minute timepoint)
 
 
 
Temperature will be recorded predose and at 60-minute intervals (±15 minutes) post-initial dose-administration, until end of the dose session
 
12-lead ECG will be performed predose and at the end of the dosing session
 

	Day 1 – Discharge	
Prior to discharge, the dosing session monitor will encourage the participant to reflect on their experience.

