Telephone Call (Visit 4)	Day 2	Participants will be contacted remotely to ensure psychological safety and for AE collection and concomitant medication monitoring and completion of the C-SSRS.
Efficacy Assessments (Visit 5)	Day 3 (+1 day)	
Central rater scales will be administered via telephone/video; the CAPS-5 (past week version) will be performed first, followed by MADRS, CGI-S, and CGI-I. The CAPS-5, MADRS, CGI-S, and CGI-I will be recorded for rater fidelity.
 
This will be followed by the participant completing the self-administered psychometric assessments (PCL-5, SDS, PGI-S, and PGI-C). The order of completion should be: Central rating scales and then the participant reported scales.

Dose Session 2 (Visit 6)	Day 8 (±1 day) – Predose	Predose assessments will be performed (including urine drugs test urine pregnancy test [WOCBP only], vital signs, temperature, 12-lead ECGs, and C-SSRS).

Treatment Period		
Study Visit	Visit Timing	Brief Description of Events
		Participants should have fasted (water only) for at least 2 hours prior to dosing and for at least 2 hours after the booster dose. (Methyl) xanthine- and caffeine-containing products should be avoided for 2 hours predose until at least 8 hours after the initial administration.

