### 4.3 Planned Duration of Study

The expected duration of participation for each participant who completes all study visits, from Screening to the EOS visit, is up to 16 weeks. The treatment duration for both Part A and Part B of the study are expected to be the same, as procedures are identical.

- Screening may take up to 28 days.

- The Baseline/Preparatory Period could last up to 4 days and should not be performed >4 days prior to Day 1.
- Enrollment confirmation will take place prior to dosing on Day 1; once enrollment has been confirmed, the Treatment Period will commence.
- The 4-week Treatment Period will consist of four dose sessions 1 week apart, with a telephone visit 1 day after each dose session for collection of safety assessments (AEs, concomitant medications, and C-SSRS) and a follow-up visit to assess safety and efficacy 2 days after each dose session.
- After the final session of the Treatment Period (Visit 14), participants will enter the Follow-Up period. Participants will attend a Follow-Up visit and a Reflection Session approximately 1, 2 and 3 weeks after the final study drug administration, followed by an EOS visit 6 weeks after the final study drug administration. Participants will also be contacted via telephone for collection of safety assessments on Day 57 ( $\pm 2$  days).
- Participants withdrawing before completion of the study should be encouraged to attend a visit that would duplicate the EOS visit to collect safety and efficacy information.

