#### 4.9 Criteria for Interruption of Randomization/Dosing of New Participants

If the following occur, enrollment/randomization and dosing of new participants will be interrupted until a DSMB review has indicated that it is safe to continue:

- 1) If there appears to be an unacceptable tolerability profile based on the nature, frequency and severity of observed AEs and/or clinical safety monitoring.
- 2) If **two** participants report Active Suicidal Ideation since last study drug administration, as evidenced by a 'Yes' response to the C-SSRS Suicidal Ideation questions 4 or 5.
- 3) If **two** participants report any suicidal behavior since last study drug administration, as evidence by a 'Yes' response to the following suicidal behavior questions on the C-SSRS:
  - a) Actual attempt, or
  - b) Interrupted attempt, or
  - c) Aborted attempt.
- 4) If **two** participants experience Grade 3 Hypertension (SBP  $\geq$ 160 mmHg or DBP  $\geq$ 100 mmHg), or Grade 2 (SBP  $\geq$ 140 mmHg or DBP  $\geq$ 90 mmHg), (as defined in the National Cancer Institute CTCAE [Version 5.0]), persisting over 48 hours post dosing, and require the need for medical intervention with more than one drug or more intensive therapy than previously used.
- 5) If **two** participants develop an abnormality of LFTs that meets the following criteria during the treatment period:
  - a) AST or ALT:
    - i)  $>$ 5-fold ULN, or
    - ii)  $>$ 3-fold ULN with concomitant serum total bilirubin  $\geq$ 2-fold the ULN with  $\geq$ 35% direct.
- 6) If **two** participants experience a clinically significant elevation of their temperature by  $>$ 2°C (and  $\geq$ 38°C) during the dosing session.
- 7) If **two** participants experience a severe psychological event related to dosing that requires an intervention.

- 8) If **two** participants experience a cardiovascular event associated with dosing that requires an intervention.
- 9) If **two** participants develop a neurological deficit.
- 10) If **three** participants experience a treatment-related SAE of any nature.
- 11) If **two** participants experience the same SAE.

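### Read literally, the liver-test rule that pauses enrolment (protocol 4.9 item 5) does not count an abnormality first found at Day 29, the only scheduled lab draw after all four dose sessions

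*Protocol*

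**What the plan says.** Protocol 4.9 lists events that stop enrolment, randomization and dosing of new participants until the DSMB has found it safe to go on. Item 5 is the liver-test item. It acts when two participants "develop an abnormality of LFTs that meets the following criteria during the treatment period". The limits are AST or ALT above 5-fold ULN, or above 3-fold ULN with total bilirubin at least 2-fold ULN and at least 35% direct.

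The period is defined elsewhere. The Synopsis heads one block "Treatment Period (Day 1 to Day 24" and the next "Follow-Up Period (Day 29 to Day 64", and SAP 3.1 uses the same days. Protocol 4.3 agrees by visit number: "After the final session of the Treatment Period (Visit 14), participants will enter the Follow-Up period". The schema in 1.2 uses a looser label, "Treatment Period (4 weeks".

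The Clinical Labs row in 1.3 has four marks: Screening, Day 15, Day 29 and the early termination (ET) visit. A footnote limits the ET mark: "Only required if the ET visit occurs prior to the Day 29 visit".

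**The concern.** Item 5 protects people who have not yet been dosed. Its purpose is served by any qualifying liver result plausibly linked to the drug, including one found after the index participant's last session. As worded, the rule stops counting at the end of the treatment period, a few days before the one scheduled sample that reflects the whole course.

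The same restriction appears in 4.8 item 8, which ends dosing for an individual. There it does no harm, because no dose follows session 4. In 4.9 it limits a rule with a different purpose.

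At stake is the only enrolment-pause rule that works on a numeric liver-test count without a judgement call. If two participants had ALT above 5-fold ULN first detected at Day 29, a literal reader would find no automatic pause.

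**Working it through.** No sample size, power or error rate is involved. The check compares the lab days with the defined period.

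**1. Scheduled draws.** Read by column, the Clinical Labs row in 1.3 marks visits 1 (Screening), 9 (Day 15), 15 (Day 29) and ET. A participant who does not leave early therefore has two on-study draws, Day 15 and Day 29.

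**2. Cross-check against the 4.2 text.**
- Day 1 list: "Predose assessments will then be performed (including vital signs, temperature, 12-lead ECGs, and C-SSRS". No labs are named.
- Day 8 list: "Predose assessments will be performed (including urine drugs test urine pregnancy test [WOCBP only], vital signs, temperature, 12-lead ECGs, and C-SSRS". No labs are named.
- Day 15 list: safety labs are named, among the pre-dose assessments.
- ET: safety labs only for those leaving before Day 29.

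The text for Days 22 and 29 is missing from the version available for review, so the absence of a Day 22 draw and the presence of the Day 29 draw rest on the 1.3 table.

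**3. Exposure behind each draw.** One session is 150 + 100 = 250 mg.
- Day 15, pre-dose: 2 × 250 = 500 mg.
- Day 29: 4 × 250 = 1000 mg.

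**4. Draw days against the period.** The first follow-up visit is Day 29 ±1, so Days 28, 29 or 30.
- Period ending Day 24: 0 of 3 permitted days fall inside.
- Period ending at Visit 14, at its latest: session 4 on Day 23, plus 2 days, plus the 1-day allowance = Day 26. Again 0 of 3.
- Period read as four calendar weeks (to Day 28): 1 of 3.

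No reading brings in a draw taken on Day 29 itself.

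**5. Could a Day 29 result be dated back into the period?** The draws are nominally 29 − 15 = 14 days apart. Of these, 24 − 15 = 9 days lie inside the period and 29 − 24 = 5 after it. With no scheduled draw between, a Day 29 finding cannot be placed on either side.

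**6. Appendix 14.1.** It lists approximately 4 hematology and 4 chemistry samples. That matches the four marks in the 1.3 row with ET included, although one person would not normally have both Day 29 and ET labs. If the 4 instead reflects an unlisted Day 22 pre-dose draw, that sample would follow session 3 and fall inside the period. It would still precede session 4, so Day 29 would remain the only scheduled draw after all four sessions.

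**7. Neighbouring rules.** In 4.9, items 2 and 3 run from the last study drug administration, and items 9 to 11 state no window. SAP 8.4.1 counts an adverse event as treatment-emergent up to 7 days after the last dose, nominally 22 + 7 = Day 29. Protocol 4.7 times Part B DSMB meetings by participants completing Day 29. Elsewhere, then, the plan treats Day 29 as relevant to drug safety.

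**The case against.** The strongest reply is that the plan already covers most of this.
- Item 1 of the same list has the same mandatory effect and refers to clinical safety monitoring. Two participants with ALT above 5-fold ULN would fit it.
- Items 10 and 11 apply if the events are SAEs, and the sponsor may suspend enrolment at any time.
- DSMB reviews in Part B fall at about every 20 participants completing Day 29, laboratory results are in the minimum data set, and ad hoc meetings are allowed.
- A clinically significant Day 29 finding would also enter treatment-emergent reporting under the SAP.

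All of this stands, and it is why the point is minor. It does not replace the count: item 1 has no number or limit, SAE status is a separate test, liver elevations are not among the listed AESIs, and scheduled reviews depend on accrual.

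A second reply is that "develop an abnormality of LFTs that meets the following criteria during the treatment period" can mean an abnormality that began by Day 24 and was seen later. That makes the rule unclear rather than clearly closed, but step 5 shows that the schedule cannot settle onset.

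A third is that the table may be imperfectly reproduced: two other rows in 1.3 show an unexpected mark at Visit 7, a telephone call, and the Day 1 and Day 8 lists need not be exhaustive. This weakens any exact statement about how many draws fall inside the period. It does not affect the finding about session 4, given step 6.

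Three stronger readings are tempting and unsupported. A reader might infer that liver abnormalities after session 2 go unmonitored; they do not, since Day 29 is drawn and reviewed, and ET or unscheduled draws by Day 24 count. A reader might infer that sites would tally the same result differently; the trigger is a study-wide count, and nothing gives sites that role. A reader might want a probability of a missed trigger; the documents give no liver event rate, and the dog study reported no hepatic damage.

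**Conclusion.** The point holds in a limited form, with minor severity. As written, item 5 does not count a qualifying liver abnormality first detected at the scheduled Day 29 draw, and no section brings that result in. For a participant completing all sessions, the sample left out is the only scheduled one after 1000 mg; the Day 15 sample reflects 500 mg.

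The gap concerns only the automatic two-participant trigger. A pause remains possible through judgement, SAE classification, the sponsor or the DSMB. Its practical size cannot be expressed as a rate.

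The conclusion rests on the Day 1 to Day 24 definition applying to item 5 and on the 1.3 table placing the post-treatment draw at Day 29. It does not depend on whether a Day 22 draw exists.

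**What to change.** In 4.9 item 5, remove the treatment-period restriction and put in its place: *at any time from first dose through the Day 29 visit (or ET visit), including unscheduled draws*. Keep the AST, ALT and bilirubin limits as they are. Leave 4.8 item 8 unchanged.

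The cost is one line in a protocol amendment, which under 12.2 needs written IRB/EC approval before use, across up to about 25 sites. It can be bundled with the next amendment. The Day 29 sample is already taken, so no procedure is added. The downside is a slightly higher chance of a temporary pause while the DSMB reviews.

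The benefit lasts only while enrolment is open. SAP 3.1 says Part B enrolment had already begun, and the documents do not say how much remained.

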## 5 STUDY TREATMENTS

### 5.1 Name and Description of Investigational Product(s)

The study interventions to be administered are detailed in [Table 3](#). Further supportive information will be provided in the Pharmacy Manual.

**Table 3: Study Interventions Administered**

Intervention Name	Methylone	Placebo (Part B)
Dose Formulation	Capsule	Capsule
Unit Dose Strength	50 mg methylone capsule	50 mg placebo capsule
Dosage Level	Initial Administration: 150 mg (3 × 50 mg methylone capsules) Booster Administration: 100 mg (2 × 50 mg methylone capsules)	Initial Administration: 150 mg (3 × 50 mg placebo capsules) Booster Administration: 100 mg (2 × 50 mg placebo capsules)
Route of Administration	Oral	Oral
Use	Investigational	Placebo

The Investigational Medicinal Product (IMP) supplied by the Sponsor or delegate is to be used exclusively in the clinical study according to the instructions in this Protocol and the Pharmacy Manual.

The Site Investigator will be responsible for storage and accountability of the IMP taking into account that methylone is a controlled substance (detailed storage/security guidance is provided in the Pharmacy Manual).

### 5.2 Study Drug Administration

Participants should have fasted (water only) for at least 2 hours prior to initial dosing and for at least 2 hours after the booster dose. Water and clear fluids will be encouraged up to a maximum of 3 liters over the dose session (see [Section 5.6](#)).

Study drug (methylone) (or matched placebo for Part B) will be orally administered on Day 1, Day 8 ( $\pm 1$  day), Day 15 ( $\pm 1$  day) and Day 22 ( $\pm 1$  day). An initial administration of 150 mg methylone (or matched placebo for Part B) will be given, followed by a booster administration of 100 mg methylone (or matched placebo for Part B) 90 ( $\pm 10$ ) minutes later.

### 5.3 Psychological and Medical Support on Dosing Days

#### 5.3.1 Psychological Support

On the dosing days, participants will be provided unstructured psychological support for at least 8 hours after the dose and until the subjective effects have subsided. The psychological support will be provided by a lead dosing session monitor (in the room) with an assistant monitor reviewing via live remote video monitoring. The lead dosing session monitor must be a licensed healthcare provider with graduate-level professional training and clinical experience in psychotherapy. The lead dosing session monitor must be licensed to practice independently.

Examples of acceptable credentials for the lead dosing session monitor are as follows:

- Clinical or counseling psychologist (PhD or PsyD)
- Psychiatrist or other physician (MD or DO)
- Master of Social Work (MSW)
- Masters Licensed Clinical Professional Counselor (LCPC)

- Licensed Marriage and Family Therapist (LMFT)
- Psychiatric Nurse Practitioner (Psychiatric NP)

Each lead dosing session monitor will undergo formal training prior to working with participants in this study. The assistant monitor must have a bachelor's degree and at least 1 year of clinical experience in a licensed mental healthcare setting.

The clinical sites will make every effort to ensure the same lead dosing session monitor will be present for all sessions with each participant. Their role will be to provide unstructured psychological support as the participant explores their response to the medication. The dosing session monitor will not be involved in any medical, nursing, or other research activities.

During the Preparatory session, the dosing session monitor will provide unstructured psychological guidance. This session will focus on psychoeducation about PTSD, possible physiological and psychological effects of methylone (including possible adverse and challenging effects), building safety for the therapeutic relationship, obtaining the background for the trauma and preparing the participant for dose sessions. Goals and expectations for the dose sessions will also be discussed.

During each dose session, the dosing session monitor will provide non-directive support of psychological well-being continuously during each dose session.

- During the early stages of the dose session, while the acute effects of methylone are active, the dosing session monitor will provide reactive support and engaged listening. The dosing session monitor will provide guidance if the participant falls into a negative pattern.
- At the end of each dose session, the dosing session monitor will encourage the participant to reflect on their experience and on any strong emotions or thoughts they might have encountered.

On Days 29, 36 and 43, post-dosing Reflection Sessions will be performed; the dosing session monitor will help the participant integrate their experiences over the four weeks of treatment, and to draw-out (if necessary) particular aspects of the experience. The dosing session monitor will assess and discuss the participant's symptoms, medical condition and psychological status/well-being following the treatment period.

Each dosing session should be recorded. The recordings will be reviewed to ensure the dosing session monitor is adhering to training and to facilitate training of future dosing session monitors.

